9.4.2 ANALYSIS OF THE PRIMARY ENDPOINT(S)

PRIMARY OUTCOME

Statistical Analysis of Primary Outcome:

1. The primary outcome will be defined as absence of any dispensing of the targeted inappropriate prescription class from day 91 to day 270 following the day of mailing. Educational interventions will be targeted towards one specific drug class so participants who switch within one class (e.g. clonazepam to lorazepam) will not be considered as having met primary outcome. **The intervention will only target one potentially inappropriate medication class for patients who are on more than one class of potentially inappropriate medication.**
2. **Timing of Ascertainment:** The timing of ascertainment is over a 6-month period beginning 3 months after mailing/intervention – i.e., we will assess evidence of a dispensing in days 91 through 270 after the date of mailing.
3. **Method of Aggregation: Hazard ratio.** The data on primary outcome will be measured as the relative hazard of time to dispensing of any new incident inappropriate prescription of

their initial drug class in the intervention vs control group. The index date for the survival analysis will be Day 91 for the trial. We chose the hazard ratio as method of aggregation as this allows the statistical analysis to account for censoring due to death or disenrollment.

4. Any prescriptions dispensed during the **blackout period** will not be counted towards measurement of the primary outcome but may affect subsequent dispensing. In covariate-adjusted survival analyses, we will adjust for whether any prescription for the same inappropriate medication class was dispensed during the blackout period and the duration of such dispensing because dispensing during the blackout period is an important factor which may affect the primary outcome. A blackout period was needed to allow time for the mailing and receipt of the intervention after randomization, and the opportunity to set up the appointment with or contact their provider to discuss the use of the potentially inappropriate medication. Alternatively, we may also consider stratification of survival analyses by prescriptions dispensed during the blackout period.

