For the primary outcome (i.e., any post-intervention discontinuation of inappropriate prescribing during the 6-month period beginning 3 months after the mailing), as a first step, we will calculate crude arm-specific percentages, as well as Kaplan-Meier curves and log-rank testing. Covariate-adjusted comparisons of arms will be estimated using Cox proportional hazards modeling. Comparing active intervention arms to usual care, we hypothesize a hazard ratio of less than 1, indicating lower risk of an inappropriate prescription in days 91-270 in the active intervention arms. The index date for the survival analysis will be day 91. We chose the hazard ratio as method of aggregation as this allows the statistical analysis to account for censoring due to death or disenrollment. To account for mortality, anticipated to be approximately 6%, we also will conduct competing risk analyses³⁰ as well as cause-specific hazards modeling.³¹

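### The adjusted hazard ratio for the primary outcome conditions on dispensing in the 90 days after mailing, and no other hazard ratio or deciding analysis is specified

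*Combined protocol and SAP*

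**What the plan says.** Section 9.4.2 item 3 makes the hazard ratio the effect measure: "The data on primary outcome will be measured as the relative hazard of time to dispensing". The clock starts at day 91 after mailing. Item 4 then says that, in the covariate-adjusted analyses, "we will adjust for whether any prescription for the same inappropriate medication class was dispensed during the blackout period". It goes on to name a second term and to give the reason for both: "and the duration of such dispensing because dispensing during the blackout period is an important factor which may affect the primary outcome". As an option it adds: "Alternatively, we may also consider stratification of survival analyses by prescriptions dispensed during the blackout period".

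The same item explains that the blackout allows the mailing to arrive and gives patients "the opportunity to set up the appointment with or contact their provider to discuss the use of the potentially inappropriate medication".

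Section 9.4.1 lists blackout renewal with age and gender as a covariate of a priori interest. It also calls for adjustment for whatever is found to predict outcomes, without limiting this to variables fixed before mailing. The same section states that all analyses are intention-to-treat.

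The closing paragraph of 9.4.2 sets out the sequence of analyses: "as a first step, we will calculate crude arm-specific percentages, as well as Kaplan-Meier curves and log-rank testing". Then: "Covariate-adjusted comparisons of arms will be estimated using Cox proportional hazards modeling". Then: "To account for mortality, anticipated to be approximately 6%, we also will conduct competing risk analyses", with cause-specific hazards models as well; no covariates are given for these.

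**The concern.** Dispensing in days 1-90 is measured after randomisation and after mailing. By the plan's own account, this is when the letter can prompt a conversation with the provider. A patient whose drug is stopped in that window because of the letter is a success of the intervention. The adjusted model compares that patient with control patients who also had no blackout dispensing, and so gives the intervention no credit for the early stop. Stratifying on the same variable does the same thing. Conditioning on it can also introduce bias from unmeasured common causes of early and later dispensing.

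Three things are at stake.

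- The only Cox comparison of arms whose adjustment is described does not estimate the total effect of assignment.
- If the log-rank test and the adjusted hazard ratio disagree, the plan has no rule for which is the result.
- Trial 1 findings may be used to drop the provider-only arm or narrow the drug classes in trial 2 (Sections 1.1 and 4.1), and the by-class analyses in 9.4.9 copy the primary analysis.

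**Working it through.** **1. Which analysis does the stated power belong to?** Inputs from Section 9.2: 4,814 × 0.901 = 4,337 per arm, so 8,674 for a pair; 13.5% censored in the window; two-sided alpha .05/3 = .0167; 80% power.

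- Events needed = 4 × 10.469 / ln(HR)², where 10.469 is the squared sum of the two normal quantiles.
- Events expected = 8,674 × mean failure proportion × 0.865, with arm 2 failure = 1 − (1 − p1)^HR.
- At p1 = 75% and HR 0.9165, arm 2 failure = 1 − 0.25^0.9165 = 0.7193. Events needed: 5,508. Events expected: 8,674 × (0.75 + 0.7193)/2 × 0.865 = 5,512.

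Solving for the hazard ratio reproduces nine of the ten rows of Table 2 within 0.0001. The 99% row computes to 0.9276 and is printed as .9267, which does not affect this point. Table 2 is thus an unadjusted log-rank calculation with no allowance for conditioning on blackout dispensing.

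**2. What does conditioning do?** The documents give no blackout renewal rate, no later failure rate by renewal, and no share of the effect that runs through blackout dispensing. Three usual-care sets were therefore assumed (renew in blackout / later failure in renewers / in non-renewers), each giving 75% overall:

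- 80/90/15%: 0.80 × 0.90 + 0.20 × 0.15 = 0.75
- 70/90/40%: 0.70 × 0.90 + 0.30 × 0.40 = 0.75
- 90/82/12%: 0.90 × 0.82 + 0.10 × 0.12 = 0.75

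The total effect is held at 75% versus 71.93%, a difference of 0.0307. A mediated share m lowers renewal in the intervention arm by m × 0.0307 / (later failure in renewers − in non-renewers). For the first set at m = 100% this is 0.0307/0.75 = 4.1 points. One common residual hazard ratio supplies the rest of the effect. A random 13.5% of patients get a uniform censoring time over the 180 days. There were 1,000 simulated trials per cell. Power means p < .0167 favouring the intervention. The adjusted model has a yes/no blackout term.

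Hazard ratio / power (%), adjusted v unadjusted, exponential failure times:

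| Share m | 80/90/15 | 70/90/40 | 90/82/12 |
|---|---|---|---|
| 0% | 0.875/99.9 v 0.904/94.0 | 0.891/97.8 v 0.910/89.6 | 0.904/93.3 v 0.913/86.0 |
| 25% | 0.901/95.9 v 0.907/91.2 | 0.915/84.9 v 0.911/88.4 | 0.924/75.4 v 0.915/86.4 |
| 50% | 0.931/64.5 v 0.913/85.9 | 0.942/49.6 v 0.915/85.1 | 0.948/39.4 v 0.919/78.7 |
| 75% | 0.964/17.3 v 0.920/78.8 | 0.971/10.1 v 0.918/81.7 | 0.973/10.2 v 0.922/75.7 |
| 100% | 0.999/0.8 v 0.926/72.8 | 1.000/1.0 v 0.922/78.0 | 0.999/0.9 v 0.926/73.0 |

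A second time shape, with failures concentrated in the first 60 days, moves the adjusted hazard ratios by at most 0.003. Adjustment raises power below a mediated share of about 31%, 21% or 13% (sets in table order) and lowers it above that. Stratifying gave the same hazard ratio as adjusting, to three decimals.

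**3. Sensitivity to the assumptions.** A second simulation assumed 85% blackout dispensing under usual care and hazards of 2.2 with and 0.35 without it per 180 days (100 trials per scenario).

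- Effect wholly through blackout dispensing (intervention arm 80%): unadjusted HR 0.925, adjusted 0.998, rejection 84% v 2%.
- Direct HR 0.9165 and no effect on blackout dispensing: adjusted 0.916 with 90% power, unadjusted 0.927 with 77%.
- Full mediation plus an unmeasured common cause: unadjusted 0.932, adjusted 1.014, slightly past the null.

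**4. Does the proposed change work?** With an assumed pre-mailing marker that shifts renewal by ±8 points, adjusting for the marker gave hazard ratios within 0.001 of unadjusted and power within 2 points. In the first set at m = 100%: 0.925 and 74%, against 0.926 and 74% unadjusted and 1.001 and 1% blackout-adjusted.

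**The case against.** The strongest reply is that a powered test of the total effect is already planned. The log-rank test does not use the covariate, and Table 2's power applies to it. That stands. What is missing is the matching effect estimate and a rule saying which result leads.

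Item 3 names no covariates, so it could be read as an unadjusted hazard ratio. The text allows that reading but does not specify it: Cox modelling of the arms is mentioned only for covariate-adjusted comparisons.

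The sizes are not derived from the plan. That is correct, and they show direction and range only. The simulated censoring also lets some censored patients fail first, giving roughly 6,050 to 6,080 events against 5,512 in Table 2. At HR 0.9165 this lifts power from 80% to about 84%, and it raises both columns. Defining the share on the log hazard ratio, so that the residual is 0.9165^(1 − m), gives adjusted power of 52% at m = 25% and 22% at m = 50%. That formula ignores the precision gained from a prognostic covariate. Mediation through duration was not simulated.

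A late blackout fill leaves supply on hand and delays the next fill, so duration is partly a matter of timing. True, but it is still measured after mailing and can still be changed by the letter.

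Limiting adjustment to pre-mailing variables also narrows the adjustment for predictors of censoring in 9.4.1. It does, but pre-mailing predictors remain available.

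**Conclusion.** The concern holds. As written, the covariate-adjusted Cox hazard ratio excludes whatever part of the effect is carried by target-class dispensing in days 1-90, whether by its occurrence or its duration. A blackout-period decision that changes dispensing only after day 90 stays in the estimate. No unadjusted or baseline-only hazard ratio is specified, and no analysis is named as deciding. These conclusions rest on the text alone.

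The size depends on the unknown mediated share. Across the three assumed sets and both time shapes, adjusted against unadjusted power is 93-100% v 86-95% at 0%, 75-96% v 86-92% at 25%, 39-65% v 79-86% at 50%, 10-17% v 76-82% at 75%, and 1% or less v 71-78% at 100%. That adjustment can gain power when little is mediated does not rescue it: the share is not known in advance, and any mediated part is lost from the estimate. This needs correcting before the primary analysis.

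**What to change.** Make a dated amendment before outcomes are seen:

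1. In 9.4.2 item 4, remove blackout dispensing, its duration and the stratification option from the primary analysis. In 9.4.1, remove blackout renewal from the a priori covariates.
2. Limit all adjustment, including the rule about characteristics found to predict outcomes, to variables fixed before mailing. Pre-mailing target-class dispensing may be among them.
3. Name one primary analysis: either the log-rank test with an unadjusted Cox hazard ratio, or a Cox model with pre-mailing covariates only.
4. Keep any blackout-adjusted or stratified model as a labelled exploratory mediation analysis. The by-arm description of days 1-90 renewal in 9.4.1 can stay, labelled as an intermediate outcome and not as a patient characteristic.

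The cost is the amendment. No patients or data are added, since dates and durations of target-drug dispensing in the six months before randomisation are already needed for the dose-reduction endpoint (9.4.3). Section 10.4 shows that trial 1 was randomised by July 2022; the documents do not say whether its outcomes have been seen. If they have, the amendment should say so, and the change still applies in full to trial 2.

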9.4.3 ANALYSIS OF THE SECONDARY ENDPOINT(S)

Secondary outcomes. These will also be assessed specific to the 6-month observation period (days 91-270 following mailing/intervention) based on health plan claims data including:

- a) Any dose reduction of each of the targeted medications, assessed at the participant level using health claims data (outpatient dispensings).
- b) Percentage of patients with prevalence of polypharmacy (defined as >5 active prescriptions for different oral agents)³²
- c) Rates of emergency room visits; rates of hospitalizations; rates of non-acute institutional stays (e.g., skilled nursing facilities); overall health care utilization (number of outpatient visits, days hospitalized, emergency department visits, and non-acute institutional days).
- d) In-hospital all-cause mortality
- e) Switching within classes

We will use administrative claims data to identify encounters of interest (ED visits, hospitalizations, non-acute institutional stays, outpatient visits) and only assess oral formulations for medications.

Measurement of Dose Reduction. We will consider dose reduction for each selected drug as being a $\geq 50\%$ decrease in the mean daily dose comparing the 6 months immediately prior to the randomization with the 6-month study window period. (day 91-day 270). We will measure average daily dose using dates of prescription dispensing, duration of prescription dispensing and strength of the prescription. We will measure the dose reduction as a dichotomous variable defined as the proportion of patients who achieved a more than 50% dose reduction in the daily dose during the study window period (day 91 to day 270) compared to the 6-month period prior to randomization. Measurement of dose reduction over 6 month follow-up requires participants to complete follow-up through end of observation period (day 270). Censored participants – that is, those who have less than 6 months in days 91-270 – will be excluded for the analysis of dose reduction. Analyses will adjust for correlates of missing data. Analyses for post-intervention polypharmacy prevalence will be analogous. We will identify participants with evidence of dispensings of ≥ 5 oral medications over the respective 6-month periods [during the study window period (day 91 to day 270) compared to the 6-month period prior to mailing]. AD medications and the three potentially inappropriate medication classes will contribute to measure of polypharmacy. Injectables and topical or ocular medications will not be counted as evidence of polypharmacy.

A combination drug will be considered a single medication for the purpose of this analysis. Additional analyses will examine within-patient change in number of inappropriate medications, where the maximum possible decrease equals the pre-intervention number of inappropriate medications. We will accommodate this between-patient heterogeneity as follows: within-patient changes will be ranked separately by pre-intervention number of inappropriate medications, ranks will be transformed using normal scores to obtain comparable distributions across these strata, and treatment arms will be compared regarding transformed ranks³⁴ using analysis of covariance. In analyses of other secondary outcomes, count outcomes such as per-patient number of emergency department (ED) visits will be analyzed using Poisson or negative binomial regression, accounting for “excess” zeros if warranted based on observed distributions.³⁵

Among study subjects who discontinue the targeted medication, we will determine if another agent within the targeted class has been dispensed over the period of observation (day 91-270). For sedative/hypnotics: dispensing of a new generic agent within the class of sedative/hypnotics. For antipsychotics: dispensing of a new generic agent within the class of antipsychotics. Analyses will be analogous to those for dose reduction.

Mortality will be analyzed using survival analyses, including Kaplan-Meier curves, log-rank testing, and Cox proportional hazards (PH) modeling, accounting for censoring due to disenrollment

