3 OBJECTIVES AND ENDPOINTS

OBJECTIVES	ENDPOINTS	JUSTIFICATION FOR ENDPOINTS	PUTATIVE MECHANISMS OF ACTION
Primary			
To assess the impact of the patient/caregiver educational intervention on inappropriate prescribing to AD/ADRD patients.	The primary outcome will be defined as absence of any dispensing of the targeted inappropriate prescription from day 91 to day 270 following receipt of intervention.	We selected this endpoint because the absence of any dispensing for the selected inappropriate drug during the study window is likely to reflect a clinically meaningful effect of the intervention.	Our research hypothesis is that education on inappropriate prescribing among patients/caregivers and their providers can reduce inappropriate prescribing in patients with AD/ADRD.
	
Secondary Outcome:
 
 a) Any dose reduction defined as a $\geq 50\%$ decrease in the mean daily dose of the targeted medication, assessed at the participant level using health claims data (outpatient dispensings). b) Percentage of patients with prevalence of polypharmacy (defined as >5 active prescriptions for different oral agents). c) Rates of emergency room visits; rates of hospitalizations; rates of non-acute institutional stays (e.g., skilled nursing facilities); overall health care utilization (number of outpatient visits, days hospitalized, emergency department visits, and non-acute institutional days). d) In-hospital all-cause mortality. e) Substitution within classes 	
We selected the endpoint of dose reduction as a secondary outcome because some of these potentially inappropriate medications require gradual taper and the effect of the intervention may only be reflected as a dose reduction. We set the threshold at 50% for dose reduction.
 
We selected the endpoint polypharmacy which has been shown to be associated with adverse outcomes in this
	Education on inappropriate prescribing among patients/caregivers and their providers can reduce medication-related morbidity in patients with AD/ADRD and lead to an improvement in medication safety for this vulnerable population.

OBJECTIVES	ENDPOINTS	JUSTIFICATION FOR ENDPOINTS	PUTATIVE MECHANISMS OF ACTION

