9.2 SAMPLE SIZE DETERMINATION

Sample Size and Power. Our target sample size for the first trial is 14,442 patients, 4814 patients in each of the three study arms. The calculations below employ 80% power, overall Type I error rate of .05 with a Bonferroni correction for 3 pairwise comparisons of study arms (.05/3=.0167), and 2-sided hypothesis testing. Based on our prior analyses,^{26,27} we anticipate death or health plan disenrollment in 9.9% of sampled patients within 3 months of the intervention (receipt of the letter), with the remaining 90.1% contributing data in the 6-month interval of interest (days 91-270 post-intervention) – that is, we anticipate a per-arm sample size of $4814 \times .901 = 4337$.

For analyses of the primary outcome, absence of dispensing of targeted inappropriate prescription classes in days 91-270, we anticipate censoring in this interval for 13.5% of participants based on prior data. To make maximal use of observed data, we will use survival analysis to model time until an inappropriate prescription (a “failure”) in days 91-270. Detectable pairwise between-arm differences (e.g., between usual care and an intervention arm) are presented in Table 2 below for a range of possible percentages for “failure” = inappropriate prescribing of the targeted drug.

Table 2. Detectable pairwise between-arm differences in hazard of inappropriate prescription classes in days 91-270

Percent with inappropriate prescribing of targeted drug (“failure”), Study Arm 1	Detectable hazard ratio for inappropriate prescribing, Arm 2 versus Arm 1
40	.8860
50	.8979
60	.9067
70	.9136
75	.9165
80	.9192
85	.9216
90	.9239
95	.9260
99	.9267

For the range of “failure” percentages examined here, which reflect those seen in Martin et al,³ detectable hazard ratios range from 0.89 to 0.93. For example, if 75% of participants randomized to Arm 1 are observed to have a “failure” (prescription for a targeted inappropriate medication) by day 270, the detectable hazard ratio for an inappropriate prescription for Arm 2 versus Arm 1 is 0.9165, a

8.35% reduction in risk; the corresponding detectable “failure” probability for Arm 2 = 0.7193, a difference smaller – i.e., more precise – than that seen in Martin et al.³ Calculations for the secondary outcome of ≥50% reduction in dose are parallel.

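### Switching is compared between arms only among participants who stopped the targeted drug, and dose reduction is worded per drug without the primary outcome's within-class switch rule

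*Combined protocol and SAP*

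**What the plan says.** **Primary outcome.** Section 9.4.2 works at the level of the drug class and states that "participants who switch within one class (e.g. clonazepam to lorazepam) will not be considered as having met primary outcome".

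**Dose reduction.** Section 9.4.3 lists "Any dose reduction of each of the targeted medications, assessed at the participant level using health claims data". The measurement paragraph begins "We will consider dose reduction for each selected drug as being a" fall of at least 50% in mean daily dose, comparing the six months before randomisation with days 91-270. Dose comes from dispensing dates, duration and strength. No rule covers within-class switches, summing across agents or dose equivalence. Participants without complete follow-up to day 270 are excluded. Section 3 chose this outcome because "some of these potentially inappropriate medications require gradual taper and the effect of the intervention may only be reflected as a dose reduction", and section 9.2 says the power calculations for a 50% "reduction in dose are parallel" to those for the primary outcome.

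**Switching.** Section 9.4.3 says "Among study subjects who discontinue the targeted medication, we will determine if another agent within the targeted class has been dispensed" in days 91-270, and then "Analyses will be analogous to those for dose reduction". Item e of the synopsis has the same restriction. A new agent is spelled out for sedative-hypnotics and antipsychotics only, not for strong anticholinergics.

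**The concern.** **Switching.** Stopping the targeted drug is what the mailing is meant to cause. If one arm has more stoppers, its discontinuer group is larger and of a different kind, so the share of switchers in it can fall although just as many people switched. A real increase in switching can be hidden in the same way. This comparison is where a reader would look to see whether stopping one agent meant starting another.

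**Dose reduction.** On a single-agent reading, someone moved from one agent to another in the same class before day 91 has a 100% reduction in the first agent. That person succeeds on dose reduction while failing the primary outcome. If switching differs by arm, part of any dose-reduction difference would be substitution and not reduced exposure to the class.

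**Working it through.** **1. The plan's own figure.** Section 9.2 gives 4,814 per arm, 90.1% still observed at day 91, 13.5% censored in days 91-270, 80% power and two-sided alpha 0.05/3 = 0.0167.
- At 75% failure and hazard ratio 0.9165, failure in the second arm is 1 - 0.25^0.9165 = 0.7193, as stated.
- Events needed (Schoenfeld): 4 x (2.394 + 0.842)^2 / (ln 0.9165)^2 = 5,509.
- Events expected: 4,337 x (0.75 + 0.7193) x 0.865 = 5,512. Power is 0.800, so the figure reproduces.

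This worked effect means 25% vs 28.07% with no dispensing of the class.

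**2. Completers.** 4,814 x 0.901 x 0.865 = about 3,752 per arm (22% of 4,814 excluded).

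**3. Switching denominator.** Let s be the share of completers who replace the index agent with another agent of the class, and d the share with no class dispensing. The discontinuers-only figure is s/(s + d). For example, 5/(5 + 25) = 16.7% and 5/(5 + 28.07) = 15.1%. All s values are assumed. The test is a two-proportion z test with pooled null variance at alpha 0.0167.

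| Switching s | Stopping d | Among discontinuers | P(significant), discontinuers | P(significant), all completers |
|---|---|---|---|---|
| 5% vs 5% | 25% vs 28.07% | 16.7% vs 15.1% | about 9% | 1.7% |
| 2% vs 2% | 25% vs 28.07% | 7.4% vs 6.7% | about 5% | 1.7% |
| 5% vs 5% | 25% vs 30% | 16.7% vs 14.3% | about 22% | 1.7% |
| 5% vs 5% | 25% vs 35% | 16.7% vs 12.5% | about 73% | 1.7% |
| 5% vs 7% | 25% vs 35% | 16.7% vs 16.7% | 1.7% | about 90% |

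**4. Which switches could score as a dose reduction.** Days 91-270 are 180 days. Assume a constant prior dose, full replacement, and uncovered days counted as zero. A switch on day t then leaves (t - 91)/180 of the prior dose. Switches by day 181 meet a threshold of at least 50%. The same paragraph also speaks of patients "who achieved a more than 50% dose reduction in the daily dose", which moves the cut to day 180. Later switches do not score.

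**5. Effect on the dose-reduction comparison.** Assume the same true class-level reduction (base) in both arms, and let a fraction f of switches score. Scored share = base + (1 - base) x f x s. The table gives the chance of a significant per-drug difference when class-level reduction is equal.

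| Base | f | Switching 2% vs 3% | 2% vs 4% | 2% vs 5% |
|---|---|---|---|---|
| 25% | 1 | 5% | 18% | 42% |
| 25% | 0.5 | 2% | 5% | 10% |
| 15% | 1 | 8% | 32% | 69% |
| 40% | 1 | 3% | 9% | 21% |

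The result depends on the scoring model. If no switcher is also a true reducer, a 25% base with 2% vs 4% switching scores 27% vs 29%, and the chance is 32%. Equal switching gives the nominal 1.7%.

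**The case against.** **The per-drug wording may be loose drafting.** The synopsis, section 3, section 8.1 and Table 2 use single-drug terms for the primary outcome, which section 9.4.2 fixes at class level. Section 6.1.2 speaks of one selected class. This stands, so the text is ambiguous and not plainly wrong. Two things favour the single agent: the switching text contrasts the targeted medication with other agents of its class, and the letters in section 6.1.1 name a specific drug.

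**Other analyses give some protection.** Section 9.4.3 also compares arms on within-patient change in the number of inappropriate medications, without restriction to discontinuers. If agents are counted, a one-for-one switch earns no decrease. The class-level primary outcome gains nothing from pure substitution either. Both are partial cross-checks: neither isolates switching nor removes switchers from the dose-reduction numerator. Section 3 and the item list in 9.4.3 name switching without the discontinuer restriction, but the only worked definitions impose it.

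**Stronger readings that the documents do not support.** A reader might infer that a positive dose result would be taken as tapering. Complete stoppers would ordinarily also meet a 50% fall, so the outcome never isolates tapering. A reader might also infer that Type I error is inflated for the outcomes as written. A per-drug difference caused by switching is a real per-drug difference, and the share among discontinuers is a true conditional proportion. The problem lies in reading either as an effect on class exposure or on switching. Finally, the 22% and 73% figures are not expected sizes: they assume stopping gaps wider than the protocol's worked example.

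**Conclusion.** The switching point holds. The planned comparison conditions on a post-randomisation subset shaped by the intervention, and this sits badly with the statements in sections 9.3 and 9.4.1 that all analyses are intention-to-treat. At the protocol's worked effect the distortion is modest: about 9% against 1.7% with 5% switching in both arms, and about 5% with 2%. It grows with the stopping gap and can also hide a real rise.

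The dose-reduction point holds in a softer form. The unit is unclear and no switch rule is stated; on the better-supported single-agent reading a switch can count as success. It creates a spurious arm difference in class exposure only if switching differs by arm, and nothing in the documents shows that it will.

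All switching rates, and the stopping rates beyond the worked example, are assumptions. Only secondary outcomes are affected; the primary outcome and the sample size stand. The change should be made before analysis, with medium confidence in its practical size.

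**What to change.** **Switching (section 9.4.3 and synopsis item e).** Compare arms among all randomised participants followed to day 270, for all three classes, using mutually exclusive categories for days 91-270: index agent only; index agent plus another agent of the class; another agent of the class only; no dispensing of the class. Keep the discontinuers-only figure as description.

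**Dose reduction (section 9.4.3).** State that it is scored at the level of the targeted class and that a within-class switch alone does not count as a reduction, matching section 9.4.2. Say whether no class dispensing counts as zero dose, and use one threshold wording throughout. These are outcome-scoring rules only.

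**Cost.** A few sentences in the plan and a small change to the claims program, using dispensings already extracted. Some true reductions among switchers will be missed. Completers remain a post-randomisation set, as the plan already accepts for dose reduction, but exclusion there follows death or loss of coverage and not stopping of the drug.
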